- 3) Psychiatric hospitalization during the course of the study if they do not have the appropriate psychiatric/behavioral health care in place locally as determined by a study physician. To be considered appropriately cared for, participants must be able to identify at least 1 mental health or prenatal provider by name and have an appointment scheduled with an outpatient provider within 10 days of being discharged.
- 4) Miscarriage or termination of pregnancy

UPWARD-S

Arm 1 Aim 1a

Inclusion Criteria

- 1) Pregnant women (prior to 16 weeks' gestation)
- 2) Age 18 or older
- 3) Presence of an ongoing community prescriber/provider
- 4) suicidal ideation as noted by item #9 of the PHQ-9
- 5) History of recurrent depression, dysthymia, or subsyndromal depression

Exclusion Criteria

- 1) Diagnosis of bipolar or psychotic disorder
- 2) Mania, psychosis, or active substance abuse (within last 6 months for substance abuse)
- 3) Non-English speaking

Drop Criteria

- 1) Inability or unwillingness to complete study procedures
- 2) Suicide attempt made during the course of the study if they do not have the appropriate psychiatric/behavioral health care in place locally as determined by a study physician. To be considered appropriately cared for, participants must be able to identify at least 1 mental health or prenatal provider by name and have an appointment scheduled with an outpatient provider within 10 days of the attempt.
- 3) Psychiatric hospitalization during the course of the study if they do not have the appropriate psychiatric/behavioral health care in place locally upon discharge as determined by a study physician. To be considered appropriately cared for, participants must be able to identify at least 1 mental health or prenatal provider by name and have an appointment scheduled with an outpatient provider within 10 days of being discharged.
- 4) Miscarriage or termination of pregnancy

Arm 1 Aim 1b

Inclusion Criteria

- 1) Age 18 or older
- 2) Current prenatal healthcare provider of a participant enrolled in Arm 1 Aim 1a

Exclusion Criteria

- 1) Non-English speaking

Arm 1 Aim 1c

Inclusion Criteria

- 1) Pregnant women
- 2) Age 18 or older
- 3) Self-reported history of major depressive disorder
- 4) suicidal ideation as noted by item #9 of the PHQ-9

Exclusion Criteria

- 1) Non-English speaking

Arm 2

Inclusion Criteria

- 1) Pregnant women (prior to 16 weeks' gestation)
- 2) Age 18 or older

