Study staff will also obtain contact information for community providers and consent from study participants to be in touch with these providers in the case of psychiatric or medical emergency and for a qualitative interview discussing their provider's experience and knowledge or caring for patients expressing suicidality. Consent to contact providers will be obtained during the baseline call for UPWARD-S after the screening questions have been asked to determine eligibility and before questionnaires are administered to assess suicidal ideation. This contact information will be used to send a letter describing the study, the qualitative provider interview, and provide the consult line and availability of study doctors for questions. This letter will be sent to providers after the baseline interview with their patient. A copy of the same letter will also be sent to the participants themselves. We will reach out to providers again when participants are in their third trimester, to remind them of their patient's participation in the study, endorsement of suicidality, and availability of study doctors for questions and consults. Additionally, we will reference the MGH Center for Women's Mental Health's website, www.womensmentalhealth.org, as a perinatal resource center that provides evidence-based safe practices for both the study participant and their clinician during pregnancy.

UPWARD-Baby

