In addition to provider interviews, medical records will be requested for the 125 women enrolled in Arm 1a. As part of the enrollment process and baseline interview, all participants will be asked to sign medical record release forms giving staff permission to obtain obstetric and labor and delivery records. Medical record release forms will be sent to participants in the mail at the mailing address that they provide. A business reply envelope will be included in this mailing to facilitate returning signed forms to study staff. The requested medical records will contain relevant vital sign measures and birth outcomes, which will be reviewed by trained study staff for abstraction of outcomes. Medical records will also be used to abstract any mention or documentation suicidal ideation and how it may have been addressed in a clinical setting. We will assess the potential relationship between suicidal ideation and behavior during pregnancy and risk for adverse obstetric outcomes (e.g., preterm labor, shorter gestational age).³⁸ We also

will assess the extent to which prenatal healthcare providers document evidence of suicidal ideation and behavior in these records; these data will inform our description of routine care of suicidal ideation and behavior is identified and addressed in routine care across a spectrum of specialty and general practice settings. Procedures for record procurement and abstraction of relevant obstetric and neonatal data are well established based on the success of the MGH team following these procedures to obtain records from over 90% of women enrolled in the National Pregnancy Registry for Psychiatric Medications.³⁹

Aim 1c.

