Participants endorsing suicidality via PHQ-9 #9 > 1 during the screening process will complete a self-report version of the Columbia Suicide Severity Rating Scale (CSSRS). Any positive endorsement of items 3-5 on the CSSRS at the time of enrollment, indicating intent or plan, will immediately trigger notification of study clinicians to initiate outreach procedures to the participant and to community provider or emergency contact. Suicidality expressed during the course of clinical and qualitative interviews, either through discussion, endorsement of suicidality on the MINI mood module, endorsement of items 3, 4, or 5 on the suicidality module of the MINI, or via scoring >2 on the MADRS item 10, will prompt study staff to complete the CS-S with the participant. A positive score on items 3, 4, or 5 of the CS-S administered by staff will also prompt a safety call by study physicians. In addition, subjects will be told by study staff to call their community providers and go to their nearest emergency room. During this risk assessment, study doctors will assess risk and recent symptoms by completing the full version of the CSSRS, collecting information about ideation, intensity of ideation, and suicidal behaviors. Outcome of this assessment will be shared with community providers.

At the time of subject enrollment for the UPWARD Supplemental Arms, participants will be notified of the outreach to their community providers during the informed consent process. Following enrollment, community providers will be sent a letter notifying them of their patient's enrollment in the study and endorsement of suicidal ideation. Aside from the information that is shared during safety outreach to community providers in the parent UPWARD study (patient name, specifics of expressing suicidal ideation - i.e. questions endorsed through self-report questionnaire, date of endorsement), no additional data collected from participants will be shared at the time of initial outreach to community providers or during the qualitative interviews with providers described in Supplemental Aim 1b. During physician safety calls, any information necessary to ensure participant safety (as determined by the study psychiatrist making the phone call) will be shared with their community provider.

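### Aim 1b takes chart documentation of suicidal ideation as routine care, but the study tells each woman's provider about the ideation, and the plan does not separate entries made before and after that notice

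*Combined protocol and SAP*

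**What the plan says.** Section V, Aim 1b, states that "medical records will be requested for the 125 women enrolled in Arm 1a". Trained staff will abstract any reference to suicidal ideation and how it was handled clinically. The investigators "will assess the extent to which prenatal healthcare providers document evidence of suicidal ideation and behavior in these records", and "these data will inform our description of routine care". Every Arm 1a woman enters with "suicidal ideation as noted by item #9 of the PHQ-9" (Section III, Arm 1 Aim 1a), before 16 weeks' gestation.

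Other sections describe what the providers are told:

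- Section VII: after enrolment, "community providers will be sent a letter notifying them of their patient's enrollment in the study and endorsement of suicidal ideation".
- Section IV, UPWARD Supplemental Arms: the letter goes out after the baseline interview, with a copy to the woman. Providers are contacted again in the third trimester "to remind them of their patient's participation in the study, endorsement of suicidality, and availability of study doctors for questions and consults".
- Section V, Prospective Follow-up and Community Outreach: providers are phoned or faxed within 24 hours when CS-S items 3 to 5 are positive. In Arm 1a the CS-S is scheduled every two weeks (Table 3).
- Section VII: consent to communicate with providers is a required part of enrolment in the parent study and is carried over to the supplement.

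Neither Aim 1b nor Section VI says that chart entries will be dated, split at the first notice or classified by source. No comparison set of charts from un-notified providers is named.

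**The concern.** The chart measure asks whether a provider identified and recorded the ideation. The study hands that same information to the provider, for every Arm 1a woman, during the period the charts cover. An entry written after the letter may show that the provider found the ideation unaided, or only that the provider read the letter. With no date or source recorded, a pooled rate cannot tell these apart.

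The background section justifies this work by how little is known about how community providers manage suicidal ideation in pregnancy, and aims to inform services and provider education. A documentation rate raised by the study's own notices, but labelled routine care, would make unaided identification look better than it is. The account of how ideation was addressed is affected too, because it would include care that followed a study notice and the offer of a study-physician consult line. The direction of that effect is less certain.

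**Working it through.** The plan gives no sample-size, precision or expected-rate figure for the chart measure, so there is nothing to reproduce. The check has three parts.

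**1. Setting the sections side by side.**

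- What is measured: provider documentation of ideation in the charts (Section V, Aim 1b).
- Who has ideation to disclose: all 125 women, by the entry criterion (Section III).
- Whose provider is told: all of them, because consent to provider contact is required (Section VII).
- When: after baseline and again in the third trimester for all (Sections IV and VII), and additionally for those with positive CS-S items 3 to 5 (Section V).
- Separation of entries by date or source: none stated (Aim 1b, Section VI).

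Entries before the first notice are unprompted. Later entries may or may not be prompted. The plan as written pools them.

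**2. How much of the record could be exposed.** Assume a 40-week pregnancy. The share of gestation after a baseline interview at week *e* is (40 − *e*)/40:

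- *e* = 8: 32/40 = 80%
- *e* = 12: 28/40 = 70%
- *e* = 16: 24/40 = 60%

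These shares are counted from the baseline interview. The letter follows it with no stated deadline, so 60% is not a lower limit on the share after the letter. Weeks are also not visits or chart entries. The figures show only that the window before notification is the shorter part of pregnancy unless the letter is much delayed.

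**3. Sensitivity of a pooled rate (assumed inputs).** Let *p0* be the share of charts that would mention ideation unprompted, and *x* the share of otherwise silent charts that gain an entry because of a notice. The pooled rate is *p0* + (1 − *p0*)*x*. The 95% half-width from sampling alone is 1.96 × √(*p0*(1 − *p0*)/125). Neither *p0* nor *x* is in the documents.

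| *p0* | *x* = 10% | *x* = 25% | *x* = 50% | half-width at *p0* |
|---|---|---|---|---|
| 10% | 19.0% | 32.5% | 55.0% | 5.3 points |
| 20% | 28.0% | 40.0% | 60.0% | 7.0 points |
| 40% | 46.0% | 55.0% | 70.0% | 8.6 points |

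Worked case: 0.20 + 0.80 × 0.10 = 0.28, a shift of 8 points, against 1.96 × √(0.20 × 0.80/125) = 7.0 points. At *p0* = 10% the smallest shift (9 points) also exceeds the half-width. At *p0* = 40% it does not (6 against 8.6), but *x* = 25% gives 15 points. The shift is systematic, so more charts would not remove it.

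**The case against.** The strongest case on the other side is that the protocol is silent on the abstraction rules rather than wrong. No abstraction form is among the documents, and the form may already record dates. The stated interest is in what providers document, so a filed study letter need not be counted as provider identification. This stands in part: the supportable statement is that no separation is stated, not that none will be made. But the routine-care label is in the plan, and followed as written the plan attaches it to the pooled entries.

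Several stronger readings are tempting and are not supported:

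- *A reader might infer that the charts as a whole record a prompted response.* Entries dated before the first notice do not.
- *A reader might infer that at least 60% of the prenatal record, and all delivery records, follow the letter and are contaminated.* The letter has no deadline, and no section says that a labor-and-delivery unit is notified. The phone or fax notice applies only to women with positive CS-S items 3 to 5.
- *A reader might infer that Aim 1b would miss the training gaps it seeks.* Aim 1b is framed mainly around what providers report, and training and support needs are assigned to the provider interviews. The charts are one descriptive component. A chart that stays silent after two notices would itself be informative.
- *A reader might infer that only pre-notification entries should be used.* That window is short. Qualifying ideation is established at study screening and may be new or not yet disclosed to any clinician, so a silent early chart may reflect no opportunity to document. A result from that window alone could be biased downward.

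**Conclusion.** The concern holds in this form: the plan describes routine care from chart entries on suicidal ideation while the study discloses the ideation to every Arm 1a woman's community provider, and it states no separation of entries before and after disclosure. The pooled documentation rate is a mixture and is probably biased upward as a measure of routine care.

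That direction rests on one assumption: notices lead to at least some entries that would not otherwise have been made, and seldom suppress entries. The documents do not allow the size to be estimated. The illustration shows that a modest prompting rate could match or exceed the sampling error, not that it will. The reach is limited to one descriptive component of a supplemental aim. The provider interviews and the parent trial's randomized comparison are not affected. This is a flaw in what the estimate means, not merely missing detail, and it is worth correcting because the correction is cheap and the records would have to be re-abstracted if dates are not captured the first time.

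**What to change.** Leave all provider notifications exactly as they are. In Section V, Aim 1b, add the following:

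1. Abstractors record the date of each chart entry on suicidal ideation and match it to a log of the first study notification and any later ones (letter, phone or fax, third-trimester reminder).
2. The study's own letter, fax or call is not counted as provider documentation, and provider entries that cite it are flagged.
3. Documentation, and how ideation was addressed, are reported separately before and after first notification, with the number of charts that have at least one prenatal visit before it.
4. Only the pre-notification result is labelled unprompted routine care. The later result is labelled care after study notification.
5. A stated limitation: the pre-notification window is short, because enrolment is before 16 weeks, and may understate routine documentation where ideation is new or not yet disclosed.

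The cost is a date and a source flag on the abstraction form, a notification log, date matching for each entry, and a few sentences in Aim 1b. The pre-notification estimate will rest on fewer visits and be less precise. The post-notification data are kept.

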all participants (at baseline, post-intervention, third trimester, 3 months postpartum, and 6 months postpartum). Participants will be offered the option to schedule phone interviews online via Calendly. Those who do not wish to use the online scheduling platform can choose to schedule directly with the study team via email, phone call, or text message on an encrypted study cell phone. Changes in medication and usage and dosage, as well as any relapse in depressive symptoms since the last phone contact, will be gauged during each phone call by study staff. Please see **Table 1** below for listing of assessments administered at each time point.

[figure not shown]

Table 1. UPWARD Measurement Schedule

UPWARD Study	Baseline	M1	W6	M2	Post-Intervention	M3	M4	M5	3T	M6	M7	M8	3PP	M10	M11	M12	6PP	12P P***
MINI full	X																	
MINI mood	X				X					X				X				X
MADRS	X				X					X				X				X
EPDS	X	X	X	X		X	X	X	X	X	X	X	X	X	X	X	X	
PHQ-8																		X
PHQ-9*	X	X	X	X		X	X	X	X	X	X	X	X	X	X	X	X	
CS-S**	X																	
CGI	X				X					X				X				X
PGI	X	X	X	X		X	X	X	X	X	X	X	X	X	X	X	X	
GAD-7	X	X	X	X		X	X	X	X	X	X	X	X	X	X	X	X	
PSS-10	X					X		X					X				X	X

WHODAS 2.0	x				x			x			x			x	
CSQ-8 (UC)	x				x									x	
CSQ-8 (MMB)					x										
CTQ	x														
PROMIS	x														
FFMQ	x		x		x									x	
RRS	x		x		x									x	
SCS	x		x		x									x	
SSQ-SF	x				x						x			x	
RSQ-MEP	x														
LEL	x													x	
LEIDS-R	x		x		x										
EQ	x		x		x									x	
CSI	x													x	
AToM	x				x			x			x			x	
PSA	x		x		x			x							
PSQI	x				x						x			x	
Positive Mood Diary	x		x		x										x
DPES Joy Subscale	x		x		x						x			x	x
CERTS Unresolution Subscale	x														
CERQ Acceptance Subscale	x														
NEO-FFI Neuroticism Domain	x														
SRET	x		x		x						x			x	x
ASQ-3											x			x	x
ASQ-SE-2											x			x	x
IBQ											x			x	x
IMP											x			x	

PSI-4-SF																x
BITSEA																x
PRFQ																x
KPCS																x
BAM-13																x
My Baby's Day																x
PAT																x
CASP																x
PANAS (post CASP; present moment instruction)																x
ECBQ																x

*PHQ-9 will also be administered every two weeks

** the CS-S will be conditionally delivered at any time point after PHQ-9 Q9 >0 or EPDS Q10 >0

*** only administered to participants that opt-in to do the additional 12-month assessment (UPWARD-Baby)

UPWARD Extension

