The final 100 participants in the UPWARD sample of 600 individuals will participate in an abbreviated version of the UPWARD procedures. These 100 women will be recruited via the same platform of BabyCenter, screened and enrolled based on the same entry criteria, and similarly randomized to the MMB intervention or Usual Care. However, the only differences will be that these final participants in this group of 100 who are randomized to the treatment group will not receive the coaching that is typically involved in the MMB intervention. This will further investigate our research aims to assess the extent to which this modified version of MMB is still an effective means of preventing depressive relapse in a perinatal population. Moreover, these final 100 participants will not receive any follow-up clinical interviews or relapse determination calls after the initial screening and baseline calls. Participants will be randomized after the baseline call, either through a phone conversation or via email. They will instead be prospectively followed through 3 months postpartum via the same battery and schedule of self-report questionnaires given to the other UPWARD participants through this timepoint. If any participant endorses items 3, 4, or 5 on the C-SSRS via these self-report questionnaires, the same suicidality safety protocol will be triggered as outlined below. The information about the delivery and newborn outcomes that would typically be collected during the 3 months postpartum interview will now be administered as a self-report survey with the rest of the questionnaires for this timepoint.

Table 2. UPWARD Extension Measurement Schedule

UPWARD Study	Baseline	M1	W6	M2	Post-Intervention	M3	M4	M5	3T	M6	M7	M8	3PP
MINI full	x												
MINI mood	x				x				x				x
MADRS	x				x				x				x
EPDS	x	x	x	x		x	x	x	x	x	x	x	x
PHQ-9*	x	x	x	x		x	x	x	x	x	x	x	x
CS-S**	x												
CGI	x				x				x				x
PGI	x	x	x	x		x	x	x	x	x	x	x	x
GAD-7	x	x	x	x		x	x	x	x	x	x	x	x
PSS-10	x					x			x				x
WHODAS 2.0	x					x			x				x
CSQ-8 (UC)	x					x							
CSQ-8 (MMB)						x							
CTQ	x												
PROMIS	x												
FFMQ	x		x			x							
RRS	x		x			x							
SCS	x		x			x							
SSQ-SF	x					x							x
RSQ-MEP	x												
LEL	x												
LEIDS-R	x		x			x							
EQ	x		x			x							
CSI	x												
AToM	x					x			x				x
PSA	x		x			x			x				
PSQI	x					x							x
Positive Mood Diary	x		x			x							

DPES Joy Subscale	x		x		x					x
CERTS Unresolution Subscale	x									

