Finally, telephone coaching is delivered for participants to accompany the MMB for Moms digital program, consistent with the coaching manual for a 12-week intervention period. Participants may also be emailed or texted by study coaches with reminders to complete sessions or to check in about progress made. These text messages will be sent from the Google Voice platform and will be limited to information needed to schedule phone calls and not for lengthy clinical discussion. The CU Boulder site will oversee the integrity of the digital MMB condition, including telephone/text/email coaching and moderating all digital site activity, including coaching feedback and online community interactions. Participants enrolled in UPWARD Extension will receive the fully functional MMB intervention but will not receive the additional coaching component.

Data describing participant engagement with the intervention will be collected and analyzed. This includes metrics captured by the MMB platform such as the number of sessions participants complete, the number of times participants log into the platform, participants' home practice completion, and participants' reflections on mindfulness practices.

Table 2

Session number	Session topic	MMB for Moms Session Objectives
1	Finding Your Place Beyond Blue	Enhancing motivation for online learning; recognizing automatic patterns of reactivity associated with perpetuation of dysphoric moods; committing to mindfulness practice as a means of stepping out of automatic pilot.
2	The Body Scan Practice	In moving attention to specific foci in the body, contrasting intentional versus automatic deployment of attention; cognitive interpretations of interpersonal events.
3	The Breath	Increasing awareness of how often the mind is busy/scattered; introducing key formal practices including mindfulness of breathing, walking, and yoga.
4	Exploring the Landscape of Depression	Increasing awareness of the ways avoidance or clinging to particular experiences can be associated with depression; practicing a new mode of responding that stays present and attentive in the face of difficulty; identifying symptoms and cognitions characteristic of depression as early warning signs.

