In UPWARD, UPWARD Extension and UPWARD-S, if suicidality is endorsed with a score of greater than 1 on EPDS item #10 or PHQ-9 item #9 or on any of the self-report questionnaires (such as the SITBI or CCM), subjects will be prompted to complete the CS-S to assess risk of suicidality. Study subjects will also be given the national suicide [contact]) and informed that answers to online questionnaires are not monitored in real time. A positive score on questions 3, 4, or 5 on the CS-S, indicating intention or plan for suicidality, will prompt a safety call by study physicians. Suicidality expressed during the course of clinical or qualitative interviews, either through discussion, endorsement of the suicidality item on the MINI mood module, endorsement of items 3, 4, or 5 on the suicidality module of the MINI, or via scoring >2 on the MADRS item 10, will prompt study staff to complete the CS-S with the participant. A positive score on items 3, 4, or 5 of the CS-S administered by staff will also prompt a safety call by study physicians. In addition, subjects will be told by study staff to call their community providers and go to their nearest emergency room. Endorsement of items 3-5 on the CS-S prompting a physician safety call has been the threshold used in previous studies at the collaborating site (University of Colorado Boulder). As this is a community-based study with collaboration from community physicians, these providers dictate treatment. We will notify community providers directly via phone or fax within 24 hours from report of positive scores on CS-S items 3-5.

VI. BIOSTATISTICAL ANALYSIS

Preliminary Analyses: Differences between the MMB and UC in demographic characteristics and depression related characteristics (e.g., symptom severity, comorbidity) will be assessed using Chi-square test for binary variables, Cochran Mantel Haenszel tests for categorical variables, and t-tests for continuous variables. Variables that show significant group differences and predict outcome will be entered in analyses as covariates; AD exposure will be included as a covariate. All participants will be considered evaluable for analysis (intent-to-treat sample). Significance levels will be evaluated at $p < .05$, and effect sizes reported.

Analysis for Specific Aim #1: To test the relative risk for depressive relapse and reduction of symptom burden between women randomized to digital MMB or UC.

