If a participant scores greater than or equal to 15 on the PHQ-9 or greater than or equal to 12 on the EPDS, the online data collection and management system (REDCap) will automatically provide participants with contact information for national mental health crisis resources and for the research study team. Study investigators will be notified immediately via an algorithm programmed into REDCap. In the UPWARD parent trial and UPWARD-S Arms 1a and 2, study staff at MGH will initiate a clinical response by phone call to assess clinical status and suicidality as soon as possible within 24 business hours of report. The score of 15 is suggested as the threshold for moderate depression.³⁹ Additionally, we will monitor specifically responses to the suicide item (#9) on the PHQ-9: 'Thoughts that you would be better off dead or hurting yourself in some way.' and the suicide item (#10) on the EPDS: 'The thought of harming myself has occurred to me' for all study participants. If a participant endorses either of these items with a score of 1 or greater, REDCap will automatically route participants to fill out the Columbia Suicide Severity Rating Scale (CS-S) and provide participants with contact information for national mental health crisis resources and for the research study team. Study investigators and staff will be automatically notified by the REDCap system for a positive score on questions 3-5 of the CS-S in order to provide outreach as soon as possible within 24 hours and assessment of the patient by a study doctor. In UPWARD-S, endorsement of current suicidal ideation on the SITBI or CCM item (#11) will also automatically route participants to fill out the CS-S. Any endorsement of items 1-5 of the CS-S will prompt administration of the full CS-S to capture duration and intensity of suicidal ideation and/or behaviors. Furthermore, any participant who misses a scheduled assessment point will be contacted immediately by study staff. Study staff will continue to try to reach participants until a participant indicates that they no longer wish to be contacted or the participant has reached six months postpartum by their estimated date of delivery, whichever comes first. Throughout the study, all participants also will be encouraged to contact the study staff at the first sign of increased depression.

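### The protocol gives two different item scores for triggering the self-report C-SSRS, and they disagree for a woman who scores exactly 1

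*Combined protocol and SAP*

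**What the plan says.** Four places in the current text give a number for the item score that sends a woman to the self-report C-SSRS:

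- **Section V, Prospective Follow-up and Community Outreach** (UPWARD, Extension and UPWARD-S): the scale is prompted "if suicidality is endorsed with a score of greater than 1 on EPDS item #10 or PHQ-9 item #9". The sentence goes on to add endorsement on other self-report questionnaires, with no number.
- **Section VII, Risks and Discomforts**, on monitoring these two items in all study participants: "If a participant endorses either of these items with a score of 1 or greater, REDCap will automatically route participants" to the C-SSRS.
- **Footnotes to Table 1 (UPWARD) and Table 2 (UPWARD Extension Measurement Schedule)**: "the CS-S will be conditionally delivered at any time point after PHQ-9 Q9 >0 or EPDS Q10 >0".
- **Section VII, on screening**: "Participants endorsing suicidality via PHQ-9 #9 > 1 during the screening process will complete a self-report version" of the scale. This names only PHQ-9 item 9.

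Two other places bear on intent without setting this trigger. The measures description in Section V gives the scale in UPWARD whenever either item is endorsed, with no number, and says UPWARD-S receives it at every timepoint. Section IV, under the Supplemental Arms, treats PHQ-9 item 9 of 1 or more as suicidal ideation.

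**The concern.** Positive answers to C-SSRS items 3 to 5 prompt the physician safety call and notification of the community provider. A woman who is not sent to the scale cannot reach that step by self-report. If the Section V wording is followed, a woman who gives the lowest positive answer is not asked by self-report about intent or plan.

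The parent UPWARD trial has other routes to detection: follow-up interviews with a staff-administered C-SSRS, relapse determination calls, a staff phone response to high totals, and coaching or other phone contacts. The Extension has far fewer. Its women "these final 100 participants will not receive any follow-up clinical interviews or relapse determination calls after the initial screening and baseline calls". On the intervention side, "Participants enrolled in UPWARD Extension will receive the fully functional MMB intervention but will not receive the additional coaching component". The staff phone response to high totals is limited by its wording: "In the UPWARD parent trial and UPWARD-S Arms 1a and 2, study staff at MGH will initiate a clinical response by phone call". The Extension's own safety provision depends on the scale having been completed: "If any participant endorses items 3, 4, or 5 on the C-SSRS via these self-report questionnaires, the same suicidality safety protocol will be triggered".

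**Working it through.** No formula in the plan is at issue. The check compares the cut-offs and then asks who is affected.

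**Step 1. Reduce the wordings to rules.** Item scores are assumed to be whole numbers.

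| Place | Applies to | Rule | Score of exactly 1 |
|---|---|---|---|
| Section V, Prospective Follow-up | UPWARD, Extension, UPWARD-S | above 1, i.e. 2 or more | not sent |
| Section VII, screening | screened women, PHQ-9 item 9 only | above 1, i.e. 2 or more | not sent |
| Section VII, REDCap routing | all study participants | 1 or more | sent |
| Table 1 footnote | UPWARD | above 0, i.e. 1 or more | sent |
| Table 2 footnote | Extension | above 0, i.e. 1 or more | sent |

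There are two rules. They disagree only for a woman whose higher score on the two items is exactly 1.

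**Step 2. Identify who is affected.** Arms 1a and 2 are not affected at scheduled follow-up, because UPWARD-S gives the scale at each timepoint. At baseline, Tables 1 and 2 mark it for everyone. What remains is post-baseline surveys in UPWARD and the Extension, and screening for women who do not go on to enrol.

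**Step 3. Check the Extension's backups.** Section VII leaves three: a call the woman makes herself, staff contact after a missed assessment, and a REDCap alert at a PHQ-9 total of 15 or an EPDS total of 12. A woman scoring 1 on the suicide item would need 15 − 1 = 14 points from the other eight PHQ-9 items, or 12 − 1 = 11 from the other nine EPDS items. She need not reach either.

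**Step 4. Count the surveys the trigger governs.**

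- Post-baseline EPDS/PHQ-9 marks: 15 in Table 1 (to 6 months postpartum) and 11 in Table 2 (to 3 months postpartum).
- Women: 600 − 100 = 500 with the full UPWARD procedures, and 100 in the Extension.
- Surveys: 15 × 500 = 7,500, and 11 × 100 = 1,100. Total 7,500 + 1,100 = 8,600.

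This is before attrition and excludes the two-weekly PHQ-9. It counts all scheduled surveys, not affected ones.

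**Step 5. Scale, as an assumption only.** The share with a highest item score of exactly 1 is not given. Section I cites 5–14% for suicidal ideation and behavior in perinatal women. If that applied here:

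- Extension: 0.05 × 100 = 5 to 0.14 × 100 = 14 women.
- All participants: 0.05 × 600 = 30 to 0.14 × 600 = 84 women.

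Those scoring exactly 1 would be some part of these.

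**The case against.** The best defence is that the rules can be followed together. Section V says the scale is prompted above 1; it does not say only above 1. Section VII is broader and describes the automated routing, so a team obeying every sentence would route at 1 or greater. The measures description and the Section IV definition of ideation fit that reading. This is good evidence of what was intended, but no text gives Section VII precedence, and Section V is the procedures text that names the Extension.

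Other points on that side:

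- **The open-ended clause on other questionnaires.** It might be read as catching any endorsement. The examples it names, the SITBI and the cross-cutting symptom measure, are not in Tables 1 or 2, and Section VII limits that routing to UPWARD-S.
- **The screening sentence.** It is a looser match. It follows text on procedures expanded for the Supplemental Arms, and no other place sets a C-SSRS cut-off for screened women who never enrol. This stands: the direct contradiction is Section V against Section VII and the two footnotes. Aligning the screening text is for consistency.
- **Table 2 marks follow-up MINI mood and MADRS for the Extension.** The Extension text, the Prospective Follow-up text and Section VII all say those interviews do not happen.
- **The two-weekly PHQ-9 asks the item again.** A later score of 2 would trigger the scale under either rule. That narrows the gap but does not help a woman who stays at 1.
- **The 5–14% range.** It describes perinatal women generally. Section IV says women with item 9 of 1 or more do not meet UPWARD criteria, and entry requires a PHQ-9 total of 9 or less. The range is therefore unsupported here in either direction and gives scale only.

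**Conclusion.** The concern holds. The current text sets two cut-offs for one safety action and leaves a woman scoring exactly 1 subject to both. The weight of the text points to 1 or greater as the intended rule. This is a wording error that should be fixed. Its practical effect depends on which rule the REDCap build follows, and the documents do not settle that by showing any missed case. The consequence is for participant safety, chiefly in the Extension. The primary analysis, power and sample size are untouched. The conclusion rests on whole-number item scoring and on the text, rather than the Table 2 marks, governing Extension interviews.

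**What to change.** 1. In Section V, Prospective Follow-up and Community Outreach, change the cut-off to 1 or greater on either item. Make the same change to PHQ-9 item 9 in the Section VII screening paragraph.
2. Confirm that the REDCap branching uses 1 or greater in UPWARD, the Extension and screening. If it does not, correct it, list the surveys where the C-SSRS was not delivered, and report them to the DSMB.
3. As a secondary clarification, state whether the above-1 cut-off in the Aim 1c procedures is intended, since the Aim 1c inclusion criterion gives no number.

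The cost is two wording corrections in an amendment and one check of the branching logic, with no new procedures.
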